#### Survival after HSCT

The treatment policy strategy will be applied. Survival after HSCT will be estimated as described below regardless of any potential intercurrent events.

Survival after HSCT is defined as time from HSCT to date of death from any cause, with censoring time at last date of contact for patients with no event ([refer to Section 6.2.2](#)). Only patients undergoing HSCT will be included in the analysis.

Survival after HSCT will be estimated applying Kaplan-Meier methodology. Median survival time, 75th and 25th percentiles will be calculated where available with associated two-sided 95% confidence intervals. Survival rates and associated two-sided 95% confidence intervals will be calculated at day 7 (1 week), day 14 (2 week), day 21 (3 week), day 30, day 60, day 100, day 180 (6 month) and day 360 (12 month).

#### Overall Survival

The treatment policy strategy will be applied. Overall survival will be estimated as described below regardless of any potential intercurrent events.

Overall survival is defined as time from first dose of emapalumab to date of death from any cause, with censoring time at last date of contact for patients with no event ([refer to Section 6.2.2](#)).

Overall survival will be estimated applying Kaplan-Meier methodology. Median survival time, 75th and 25th percentiles will be calculated where available with associated two-sided 95% confidence intervals. Survival rates and associated two-sided 95% confidence intervals will be calculated at day 7 (1 week), day 14 (2 week), day 21 (3 week), day 30, day 60, day 100, day 180 (6 month) and day 360 (12 month).

### **6.9. Exploratory Analysis**

### **6.10. Safety Analysis**

All safety analyses will be based on all treated analysis set.

#### **6.10.1. Adverse Events**

Detailed information on AEs occurring after the first dose of investigational medication until EOS including adverse event term, start data and time, end date and time, outcome, maximum severity, relationship to IMP and potential causative factors, whether the AE caused study discontinuation, answer indicating whether the event is a SAE, and criteria met for SAE will be collected in the CRF. All AE records collected will be included in the analysis. Adverse event terms will be standardized using the latest updated English version of MedDRA.

An adverse event will be considered treatment-emergent if the start date and time of the event are equal to or later than the date and time of first infusion (otherwise pre-treatment event). For determination of treatment-emergent AEs with presence of missing data, please refer to [Section 6.2.1](#).

Besides secondary analyses described in [Section 6.8.1](#), the overall incidence of TEAEs related to study drug (non-serious related AEs) and serious TEAEs related to study drug will be summarized at event level and subject level by SOCs and PTs.

In addition, the incidence of treatment-emergent AEs and treatment-emergent SAEs will be tabulated by SOCs and PTs based on maximum severity.

The overall incidence of all AEs, treatment-emergent AEs, treatment-emergent SAEs, severe treatment-emergent AEs, infusion-related AEs, infection-related AEs, treatment-emergent AEs related to study drug, severe treatment-emergent AEs related to study drug, all SAEs, treatment-emergent SAEs, serious treatment-emergent AEs related to study drug, infusion-related SAEs, infection-related SAEs, AE leading to treatment temporarily interrupted related to study drug, AEs leading to treatment permanently discontinued related to study drug, AEs leading to study withdrawal and AEs leading to death at event level and subject level will be tabulated in a summary table. In addition, AEs occurred prior to HSCT and after HSCT will be similarly tabulated.

For all treatment-emergent SAEs, the incidence will be tabulated at event level and subject level by criteria met in a summary table.

Listings will be provided for all AEs, SAEs, AEs resulting in study discontinuation, AEs resulting in death, infusion-related AEs, infection-related AEs, and AEs leading to treatment temporarily interrupted/treatment permanently discontinued related to study drug.

### **6.10.2. Laboratory Test Results**

Data on the test item(s), result, clinical significance, unit, normal range limits, and additional comments for hematology, biochemistry, coagulation, sCD25, urinalysis, and cerebrospinal fluid (CSF) analysis (if clinically indicated) will be documented in the CRF. Laboratory test data will be collected at all scheduled visits for the treatment period and the follow-up period.

The numeric findings of laboratory test result (including hematology, biochemistry, coagulation, sCD25, CSF analysis, and urinalysis) will be summarized for screening visit and following visits using descriptive statistics. Actual values and actual changes from baseline will be presented. Qualitative clinical evaluation (normal, not clinically significant, clinically significant, or not done) will be tabulated for screening visit and presented using shift table for following visits. CSF analysis will only be tabulated for subjects with available baseline CSF analysis results and available CSF results for at least one post-treatment visit.

Listings will be provided for all laboratory data collected for scheduled and unscheduled visits. In addition, all abnormal laboratory findings of subjects with normal result at baseline will be listed.

### **6.10.3. 12-Lead Electrocardiogram**

Clinical evaluation of 12-lead ECG (normal, not clinically significant, or clinically significant) will be collected at screening, week 8, and EOT visit during treatment period.

Clinical evaluation will be tabulated for screening visit and presented using shift table for each applicable scheduled visit. Listings will be provided for all ECG data collected for scheduled and

unscheduled visits. In addition, all abnormal ECG findings of subjects with normal result at baseline will be listed.

#### **6.10.4. Other Safety Results**

##### Vital signs

Numeric result and clinical evaluation (normal, not clinically significant, or clinically significant) of body temperature, heart rate, blood pressure (BP), and oxygen saturation will be collected in the CRF for all visits. Body temperature will be measured pre-infusion, at the end of the infusion, 1 hour and 2 hours after the end of each infusion. Oxygen saturation will be measured every 30 minutes during the infusion, at the end of infusion and 1 and 2 hours post-infusion. For the first infusion, oxygen saturation will be measured continuously during the infusion and up to 2 hour post-infusion. For the first infusion (or the first infusion after an increased dose) BP and heart rate will be measured every 15 minutes during the infusion, at the end of infusion and 1 and 2 hours post-infusion. For EOT and subsequent follow-up visits, if no infusion-related reactions have occurred, BP and heart rate will be measured every 30 minutes, at the end of infusion and 1 and 2 hours post-infusion.

Body temperature, heart rate, BP measurements, and oxygen saturation will be summarized for screening visit and each planned time point for the following scheduled visits using descriptive statistics. Actual values and actual changes from baseline will be presented. Clinical evaluation will be tabulated for screening visit and presented using shift table for following scheduled visits. Listings will be provided for all vital signs data from scheduled and unscheduled visits. In addition, all abnormal vital signs findings of subjects with normal result at baseline will be listed.

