4.3.2 Potential risks based on emapalumab’s mechanism of action

Infusion related reactions and hypersensitivity:

IRRs are commonly associated with monoclonal antibody infusions and are defined as signs or symptoms with a temporal relationship to the administration of an infusion and assessed as related, typically occurring soon after the start of the infusion, although symptoms may be delayed for up to 24h. They might be limited (skin reaction) or systemic.

Cumulatively, among 108 subjects receiving emapalumab in clinical trials up to safety data cut-off point of 24-Aug-2020, no patient experienced anaphylactic or anaphylactoid reaction, including:

- Study NI-0501-03: Of 20 healthy volunteers participating in the study, 6 emapalumab and 2 placebo-treated subjects experienced IRRs. IRRs in subjects receiving emapalumab included ventricular tachycardia, paraesthesia, feeling cold, pyrexia, myalgia, and headache
- Study NI-0501-04: Of 45 patients participating in the study, a total of 12 patients (26.7 %) experienced at least one IRR. All were non-serious and, except for one which was moderate, all were mild and none of them led to emapalumab discontinuation. The majority were skin reactions (drug eruption 8.9 %; rash, 4.4 %; erythema, 4.4 % rash erythematous 2.2 %), hyperhidrosis (8.9 %), pyrexia (6.7 %), tachycardia (2.2 %) and lymphadenopathy (2.2 %).
- Study NI-0501-09: Of 26 patients participating in the study, one IRR (acute respiratory failure) was reported as serious, occurring during 8th emapalumab infusion, leading to permanent emapalumab discontinuation; it resolved with appropriate treatment. Two (2)

additional, non-serious IRRs of sinus tachycardia, one mild and one moderate were reported, both of which recovered within 24 hours.

From the clinical experience to date, the risk of IRRs associated with emapalumab treatment seems to be very low. Nevertheless, the infusion should be performed under medical supervision with monitoring of vital signs during and for 2 hours after emapalumab infusion as outlined in Section 6.5.6.1

Infections:

As emapalumab neutralizes IFN γ activity, emapalumab may increase the risk of infections caused by some specific pathogens potentially favored by IFN γ neutralization including mycobacteria (typical and atypical), salmonella, varicella zoster virus (VZV), and *Histoplasma capsulatum*. Study specific requirements should be followed for infections screening, prophylaxis, and monitoring.

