11.1 At patient level

11.1.1 Decision to Slow Down or Stop Emapalumab Infusion due to Systemic Reaction

During the infusion of emapalumab, any significant change compared to pre-infusion values in vital signs, such as those listed below, should trigger appropriate immediate care:

- Sudden and sustained increase or paradoxical decrease of heart rate (duration of more than 5 minutes) compared to pre-infusion value and not linked to child's anxiety or fear;
- Sustained (an episode of more than 5 minutes duration or more than 3 episodes of shorter duration, i.e., 3 minute) oxygen desaturation (below 90%);
- Any clinical sign or complaint indicative of patient distress

The decision to interrupt the infusion might be taken by the investigator in the event of any of the above-mentioned occurrences.

The decision to restart the infusion will be based on the evolution of the patient's status (i.e., resolution of symptoms after appropriate symptomatic measures, e.g., oxygenation or administration of anti-histamine treatment), and upon investigator's own medical judgment. The infusion will generally be restarted at a lower rate.

All changes in infusion rate will be recorded in the patient's medical chart and the eCRF each time there is a rate modification, as well as at the end time of premature or delayed termination of the infusion.

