Baseline will be defined as the last available measurement or recording prior to the first study drug administration. For assessments performed only on screening visit prior to the first emapalumab infusion, the measurement or the recording of the screening visit will be used as baseline. For

assessments that are also performed pre-infusion on visit 1 in addition to screening visit, the measurement or recording pre-infusion on visit 1 will be used. If the measurement or recording pre-infusion on visit 1 is not available, then the measurement or recording of the screening visit will be used.

Unless otherwise noted, descriptive statistical summary will only include data from scheduled visits or time points. Data from unscheduled visits or time points will be presented in data listings. For data of quantitative measurements but are collected with characters such as “>/≥” or “</≤”, the numeric part of the value will be used in the descriptive analysis. For other cases where characters are entered for quantitative measurements, the result will not be used in the descriptive analysis but only included in data listing.

If deemed necessary, specific data points may be excluded from the analysis based on related discussion in the data review meeting (DRM). The decisions and reason(s) for exclusion will be documented separately in Resolution of Data Review Meeting in detail.

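### After the first infusion, vital-sign change scores use only the visit 1 (or screening) value as reference, so they mix the acute infusion effect with change in disease state

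*SAP*

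**What the plan says.** SAP 6.1 sets one baseline per patient: "Baseline will be defined as the last available measurement or recording prior to the first study drug administration". Where an assessment is done at screening and again before the first infusion, "the measurement or recording pre-infusion on visit 1 will be used". The fallback is: "If the measurement or recording pre-infusion on visit 1 is not available, then the measurement or recording of the screening visit will be used".

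SAP 6.10.4 applies this to vital signs. The readings "will be summarized for screening visit and each planned time point for the following scheduled visits using descriptive statistics", and "Actual values and actual changes from baseline will be presented". The clinical evaluation goes into shift tables. All vital signs are listed, and there is a further listing of abnormal findings in subjects who were normal at baseline.

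For temperature, the SAP names the reference reading explicitly: "Body temperature will be measured pre-infusion, at the end of the infusion, 1 hour and 2 hours after the end of each infusion". For heart rate, blood pressure and oxygen saturation, the SAP and protocol 6.5.6.1 name readings during, at the end of and after the infusion. A pre-infusion reading of these signs rests on the pre/post label in protocol Table 3, and the week 8 cell carries no such label.

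Protocol 4.3.2 asks for "monitoring of vital signs during and for 2 hours after emapalumab infusion" because of infusion-related reactions. Protocol 11.1.1 makes "any significant change compared to pre-infusion values in vital signs" a trigger for immediate care. Neither document defines an analysis of change from the same visit's pre-infusion value.

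**The concern.** The serial readings around each infusion are there to pick up infusion reactions, and the natural contrast is during or after versus just before. The SAP's only change score uses a reference that, by week 8, is eight weeks old. Patients enter with active HLH. Fever is a typical feature of the disease and its resolution is a response criterion, so temperature can be expected to move between visit 1 and later visits for reasons unrelated to the infusion. Heart rate may do the same.

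The later infusions matter. Dose increases start at visit 2, so the first infusion at an increased dose is always among them, and protocol 6.5.6.1 calls for 15-minute blood pressure and heart rate readings at those infusions. The serious infusion reaction reported from study NI-0501-09 came at the eighth infusion. Pyrexia and tachycardia are among the reactions reported in protocol 4.3.2. With 10 to 18 patients, the safety signal is more likely to be one patient's outlying rise than a shift in a mean.

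**Working it through.** The documents give no figure on this point, so there is none to reproduce. The check traces the SAP 6.1 baseline into SAP 6.10.4.

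**1. What the change score contains.** Let B be the study baseline, P the pre-infusion reading at a given visit, and Q a reading during or after that infusion. The SAP tabulates Q and Q − B, where

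Q − B = (P − B) + (Q − P).

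The first term is drift since visit 1 and the second is the acute change. At visit 1, P = B (unless that reading is missing), so the score is already the acute change.

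**2. How many infusions.** At two a week:
- 8 weeks: 2 × 8 = 16 infusions, 15 after the first, 15/16 = 93.8%.
- 26 weeks (about the six months that the protocol recommends not exceeding): 2 × 26 = 52, 51 after the first, 51/52 = 98.1%.

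These are infusions at which the two contrasts can differ. They are not a count of errors: with no drift the contrasts agree, and at visit 2 only 3 to 4 days have passed.

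**3. Heart rate (assumed values).** For an acute rise of +30:
- drift 0: score = 0 + 30 = +30
- drift −20: score = −20 + 30 = +10
- drift −40 (150 at visit 1, 110 before and 140 after the later infusion): score = 140 − 150 = −10

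**4. Temperature (assumed values).** SD 0.6°C at visit 1, 0.4°C for later pre-infusion readings, 0.2°C for the within-infusion change, all independent.

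| Drift | Acute rise | Mean Q − B | Mean Q − P |
|---|---|---|---|
| 0 | +0.5 | +0.5 | +0.5 |
| −1.0 | +1.0 | 0.0 | +1.0 |
| −1.5 | +0.5 | −1.0 | +0.5 |

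SD of Q − B = √(0.36 + 0.16 + 0.04) = √0.56 = 0.75. SD of Q − P = 0.20. A simulation gave the same values. Positive correlation between a patient's visit 1 and later readings would lower the 0.75.

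**5. What the planned tables still allow.** If the same patients contribute, mean(Q − B) − mean(P − B) = mean(Q − P). In the last line of step 3, −10 − (−40) = +30. Medians and ranges do not subtract in this way, and the SD of Q − P needs the covariance of P and Q, which is not tabulated.

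**6. Counts of abnormalities.** SAP 6.8.1 treats a vital sign abnormality as treatment-emergent if it was absent at baseline. Read literally, a fever present at visit 1 that settles and returns during a later infusion is not counted. Take 37.5°C (the SAP's no-fever limit for response) as a stand-in for abnormal, and keep the SD and independence of step 4. The share of acute fevers counted then equals the share of patients below 37.5°C at visit 1:
- visit 1 mean 37.0: Φ(0.5/0.6) ≈ 80%
- visit 1 mean 38.0: Φ(−0.5/0.6) ≈ 20%
- visit 1 mean 38.5: Φ(−1.0/0.6) ≈ 5%

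**The case against.** A reader might infer that the plan hides infusion effects. It does not. Actual values are shown at each planned time point, so a table holding 110 before and 140 after shows the rise, and the mean acute change follows by subtraction. All vital signs are listed, which is manageable with at most 18 patients.

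Infusion reactions also have their own route. Protocol 4.3.2 defines them as signs or symptoms assessed as related, which is an adverse-event concept. Clinically significant vital signs are reported as AEs. AEs from infusion start to 24 hours are handled separately, and SAP 6.10.1 tabulates and lists them.

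A reader might also infer that every infusion is compared with the wrong reference, or that the SAP contradicts protocol 11.1.1. The first infusion is compared correctly unless its pre-infusion reading is missing. Section 11.1.1 is a bedside trigger and not an analysis definition, so there is no contradiction. The SAP simply does not summarise the contrast that is used at the bedside.

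All of that stands, and it limits the point without removing it. Subtraction recovers only a mean. The AE route depends on the investigator judging a reading clinically significant, on accompanying symptoms or on an intervention. Its 24-hour window covers about 2 of every 7 days at two infusions a week, so it is not specific to acute change. The listings hold the data but leave the calculation to the reader.

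**Conclusion.** The point holds in a limited form. For infusions after the first, the only change score for readings during and after infusion mixes the acute effect with change in disease state. The SD, median, range and individual outliers of the acute change are not summarised. Actual values, listings and infusion-related AE tables give partial information.

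The size for any one reading equals the drift, P − B. It is zero without drift, and enough to reverse the sign when drift is opposite to the acute change and larger. The heart rate and temperature figures are assumed illustrations, as are the 80%, 20% and 5% shares. The documents give no data from which to estimate drift.

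A reader might take this as a flaw in the primary analysis. The documents do not support that: the primary endpoint is discontinuation for drug-related AEs, and no hypothesis is tested. What is affected is the descriptive vital-sign output that supports the primary safety objective. The change should be made because it is cheap and uses data the schedule largely already collects.

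**What to change.** In SAP 6.10.4:
- Keep the change from study baseline.
- For all time points during and after infusion, add the change from the same visit's pre-infusion value, summarised by infusion and time point.
- Add a count or listing of abnormalities that were absent before infusion at that visit.
- State that the pre-infusion reading of heart rate, blood pressure and oxygen saturation at each infusion visit, week 8 included, is the reference. The SAP now says this only for temperature.
- Keep any breakdown by dose level purely descriptive. Dose is increased on unsatisfactory response, so dose level is confounded with disease state, and the cells would be sparse.

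The same paragraph places the 30-minute and end-of-infusion readings of blood pressure and heart rate at EOT and follow-up visits, while protocol 6.5.6.1 refers to subsequent visits. The two need reconciling so that the planned time points are clear.

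The cost is one extra derived baseline flag and some added tables. Table 3 already labels vital signs pre and post infusion at the infusion visits other than week 8, so the one point to confirm is that the week 8 reading is taken before infusion.

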##### Physical Examination

Clinical evaluation (normal, not clinically significant, clinically significant, or not done) of a complete physical examination (including spleen size, liver size, general appearance of the skin, neurological status, head, ears, eyes, nose and throat, lungs, cardiac, abdomen, musculoskeletal system and other) will be collected for the screening visit in the CRF. For all other scheduled visits, results of a brief examination (including spleen size, liver size, general appearance of the skin, neurological status and other) will be collected in the CRF.

Clinical evaluation will be tabulated for screening visit and presented using shift table for following scheduled visits.

Listings will be provided for all physical examination data from scheduled and unscheduled visits. In addition, all abnormal physical examination findings of subjects with normal result at baseline will be listed.

##### Imaging

The result of abdominal ultrasound, chest x-ray or chest CT (computed tomography), and brain MRI (Magnetic resonance imaging) or brain CT or cranial ultrasound if clinically indicated will be collected at the screening visit. Abdominal ultrasound will be performed every two weeks during the treatment period, and at the pre-conditioning visit, D+100 visit and the EOS visit of the follow-up period. For the treatment period and the follow-up period, chest and brain imaging (chest x-ray or chest CT, and brain MRI or brain CT or cranial ultrasound) will be performed if clinically indicated.

Longitudinal length of the spleen measured from abdominal ultrasound will be summarized using descriptive statistics for screening visit and all scheduled visits. Actual values and actual changes from baseline will be presented. Clinical evaluation of available imaging results (normal, not clinically significant, or clinically significant) will be tabulated for screening visit and presented using shift table for applicable scheduled visits. Chest imaging will only be tabulated for subjects with available chest X-ray or chest CT result from at least one post-treatment visit. Brain imaging will only be tabulated for subjects with available baseline brain MRI or brain CT or cranial ultrasound result and available brain imaging result from at least one post-treatment visit.

Data listing will be provided for all imaging data from scheduled and unscheduled visits. In addition, all abnormal imaging findings of subjects with normal result at baseline will be listed.

